# 1.0 STUDY SYNOPSIS

This is an investigator initiated, open label trial of defibrotide for therapy of patients with SARS-CoV2 related acute respiratory distress syndrome (ARDS). The primary endpoint is safety and tolerability. Secondary endpoints will assess response and ventilator free survival.

*Eligibility*: Patients ≥ 18 years in age with evidence of SARS-CoV2 related ARDS. All patients must exhibit signs of coagulopathy evidenced by a D-dimer > 2X ULN.

**Study therapy:** Defibrotide will be administered intravenously (IV) every 6 hours (Q6H) for 7 days of therapy. Patients who meet defined toxicity and/or efficacy criteria within the 7-day period may cease study therapy at that earlier time point. Patients with a partial response to study therapy by day 7 (defined as > 20% decrease in supplemental oxygen) may continue to receive an additional 7 days of therapy (14 days total therapy). Toxicity (including rate of hemorrhage / bleeding) will be assessed. Each patient will be monitored for 14 days, including 7 days of therapy and 7 days of post-therapy observation.

**Sample Size:** 12 patients. An interim assessment for toxicity and early mortality will be performed after the first six patients have enrolled. Accrual may proceed to a maximum of 12 patients, if the stopping rules are not met within the first six patients.

**Other:** The study will target patients with either early or late-phase ARDS, provided patients have not required mechanical ventilation for > 7 consecutive days. The study allows co-enrollment with other SARS-CoV2 therapy trials, provided those trials are not also utilizing other anti-coagulant or fibrinolytic agents.

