# 8.3 Primary stopping rule

An incidence of > 20% hemorrhagic complications would be unacceptable in this setting. Thus, we will continually monitor the observed proportion of patients with major bleeding complications. We start with prior Beta(2,8) distribution, which has mean 0.2. If ever we have more than 80% posterior probability that the true proportion is greater than 0.20,

accrual to the protocol will be suspended to allow the DSMB to review the incidence of major bleeding.

Specifically, if we see at least **three** patients with major bleeding among the first six patients, or at least **four** patients with major bleeding among the first eleven patients, the study will be suspended. If the true proportion of major bleeding events is 0.20, the study has a probability of 0.19 of being suspended. If the true proportion of major bleeding events is 0.30 or 0.40, the probability of trial suspension is 0.47 and 0.73, respectively. Note that if the trial is suspended to accrual, the accrual is expected to be seven patients.

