# 8.4 Secondary endpoints

There are two secondary endpoints: (i) Day 14 overall survival and (ii) Day 14 ventilator-free survival, both of which are binary endpoints. Day 14 overall survival will be summarized by the proportion of the twelve patients who are alive at Day 14 after starting treatment, and Day 14 ventilator-free survival will be summarized by the proportion of the twelve patients who are both alive and not using a ventilator at Day 14 after starting treatment. Both proportions will be accompanied by an exact 95% confidence interval.

We will also continually monitor the study for excessive Day 14 mortality. In parallel with our decision rule related to excessive severe hemorrhagic events, we will suspend accrual if we see if we see at least five deaths by Day 14 among the first six patients, or at least seven deaths by Day 14 among the first eleven patients. If the true Day 14 mortality rate is 70% (which is the historical rate for patients with respiratory comprise), the study has a probability of 0.80 of being suspended. Conversely, if the Day 14 mortality rate is 50%, the study has a much lower probability of 0.30 of being suspended.

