# 11.0 DATA SAFETY MONITORING:

Protocol Monitoring Committee: A protocol monitoring committee consisting of the principal investigators, one or more co-investigators, study coordinator, and data manager will meet monthly during the conduct of the study to discuss expected and unexpected adverse events, safety concerns, adherence to protocol therapy, study enrollment, and any potential protocol amendments that may be required. Recommendations for study continuation, amendments, suspension and/or study termination will be made at each of the monthly protocol monitor meetings and formally submitted to an independent Data Safety Monitoring Board.

Data Safety Monitoring Board (DSMB): Membership shall consist of two external (non-Michigan Medicine) and two internal (Michigan Medicine) physicians. The DSMB will be an independent body, with none of the DSMB members serving as study co-investigators. The DSMB will meet quarterly to review the conduct of the study, including review of all monthly reports submitted from the protocol monitoring committee. More frequent DSMB meetings may be required, pending any issues raised in the monthly reports from the protocol monitoring committee. In addition, the DSMB will review the study after the first 6 patients have completed study drug therapy, to determine if the study stopping rules for early termination have been met, and if the study enrollment should be terminated or allowed to continue. Enrollment will be held once the 6th patient has completed study drug therapy, to allow the DSMB to make this determination. Reports from the DSMB meetings will be furnished to IRBMED in accordance with Michigan Medicine policies.

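### The synopsis and Section 11 tie the stopping rules to the first six patients only, while the suspension probabilities printed in Sections 8.3 and 8.4 also need the eleven-patient boundary

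*Combined protocol and SAP*

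**What the plan says.** Section 8.3 monitors the proportion with major bleeding continually. Accrual is suspended for DSMB review if three of the first six patients bleed, or if there are at least four "patients with major bleeding among the first eleven patients, the study will be suspended". The stated suspension probabilities are 0.19, 0.47 and 0.73 at true rates of 0.20, 0.30 and 0.40. It adds: "Note that if the trial is suspended to accrual, the accrual is expected to be seven patients".

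Section 8.4 monitors Day 14 mortality continually, in parallel. Accrual is suspended at five deaths in the first six, or "at least seven deaths by Day 14 among the first eleven patients". The stated probabilities are 0.80 at 70% mortality and 0.30 at 50%. This section does not mention the DSMB.

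The synopsis describes one look: "An interim assessment for toxicity and early mortality will be performed after the first six patients have enrolled". It continues: "Accrual may proceed to a maximum of 12 patients, if the stopping rules are not met within the first six patients".

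Section 11 ties one review, and one enrolment hold, to these rules. Its sentence on the review begins: "the DSMB will review the study after the first 6 patients have completed study drug therapy, to determine if the study stopping rules". Otherwise, "The DSMB will meet quarterly to review the conduct of the study, including review of all monthly reports submitted from the protocol monitoring committee". It also allows that "More frequent DSMB meetings may be required, pending any issues raised in the monthly reports from the protocol monitoring committee".

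No section schedules a review or hold at eleven patients, or says that enrolment waits for 14-day outcomes after the six-patient review.

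**The concern.** The sections that staff and the DSMB will use to run the trial describe the rules differently from the statistical section. Someone working from the synopsis and Section 11 could enrol to twelve after a clean six-patient review without applying the second boundary. Safety is the primary objective and bleeding within 14 days of starting treatment is the primary endpoint, so what is at stake is the monitoring of patients 7 to 12.

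Two gaps add to this. First, the only action stated in Sections 8.3 and 8.4 is suspension of accrual. Once patient 12 has enrolled there is no accrual left to suspend, although patients may still be inside their 14-day window. Second, the printed probabilities and the expected accrual of seven are computed as if each patient's outcome were known before the next patient enters.

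**Working it through.** **Inputs.** Bleeding boundaries r1 = 3 of 6 and r2 = 4 of 11 (Section 8.3). Mortality boundaries r1 = 5 of 6 and r2 = 7 of 11 (Section 8.4). True rates p as printed there. The endpoint window is 14 days (Section 8.1).

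**Step 1: reproduce the printed figures.** With X6 the events in patients 1-6 and X5 the events in patients 7-11,

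P(suspend) = P(X6 ≥ r1) + Σ over x < r1 of P(X6 = x) · P(X5 ≥ r2 − x).

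Bleeding at p = 0.30:
- First boundary: P(X6 ≥ 3) = 0.2557.
- Second boundary: 0.1176 × 0.0308 + 0.3025 × 0.1631 + 0.3241 × 0.4718 = 0.0036 + 0.0493 + 0.1529, which is 0.2059 before rounding of the terms.
- Total: 0.4616. The second boundary's share is 0.2059 / 0.4616 = 45%.

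Mortality at p = 0.70:
- First boundary: P(X6 ≥ 5) = 0.4202.
- Second boundary (x = 0 and x = 1 cannot reach seven): 0.0595 × 0.1681 + 0.1852 × 0.5282 + 0.3241 × 0.8369 = 0.0100 + 0.0978 + 0.2713 = 0.3791.
- Total: 0.7993. The share is 0.3791 / 0.7993 = 47%.

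| Rule, true rate | Printed | Both boundaries | Six-patient look only | Added by second boundary | Its share |
|---|---|---|---|---|---|
| Bleeding 0.20 | 0.19 | 0.188 | 0.099 | 0.089 | 47% |
| Bleeding 0.30 | 0.47 | 0.462 | 0.256 | 0.206 | 45% |
| Bleeding 0.40 | 0.73 | 0.725 | 0.456 | 0.270 | 37% |
| Mortality 0.70 | 0.80 | 0.799 | 0.420 | 0.379 | 47% |
| Mortality 0.50 | 0.30 | 0.293 | 0.109 | 0.183 | 63% |

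All five printed values are reproduced to within 0.01, and only with the second boundary in force. A patient-by-patient recursion gives the same totals. In it, mean enrolment at suspension is 7.4, 7.1 and 6.6 at bleeding rates 0.20, 0.30 and 0.40, which agrees with the printed seven.

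**Step 2: where the second boundary acts.** With immediate outcomes, the bleeding boundary is crossed at patients 7-10 with probability 0.056/0.139/0.198, and exactly at patient 11 with 0.034/0.067/0.072. For mortality at 70% and 50%, the figures are 0.256/0.093 and 0.123/0.090. So it does not work as a single look at eleven. It needs counting throughout accrual of the second half.

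**Step 3: allow for the 14-day window.** The protocol gives no accrual rate, so this step rests on assumptions: 0.5 to 3 patients per week arriving at random, bleed onset uniform over 14 days, the printed counts applied as each bleed occurs, and a short pause or none around the six-patient review. Simulation then puts the probability of crossing before patient 12 enrols at roughly 0.10-0.17, 0.29-0.43 and 0.52-0.69 for true bleeding rates 0.20, 0.30 and 0.40, against 0.19, 0.47 and 0.73 printed. Slow accrual gives values near the printed ones and fast accrual gives the lower ends. Mortality was not simulated, but the same lag works in the same direction.

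**The case against.** The best defence is that Section 8 is the operative text and is adequate. Section 8.3 monitors bleeding continually and sends a crossing at any patient number to the DSMB. Section 8.4 monitors deaths continually, in parallel. Section 11 adds monthly committee recommendations submitted to the DSMB, quarterly DSMB meetings and extra meetings if needed. The synopsis wording is permissive and sets a ceiling; it does not say that monitoring ends at six. The six-patient-only probabilities therefore describe a procedure that Section 8 does not prescribe. Computing such probabilities with immediate outcomes is a common simplification, and the size of the lag effect depends on inputs the protocol does not give.

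Most of this stands, and it rules out two stronger readings. A reader might infer that the eleven-patient boundary gets no DSMB look. That is wrong for bleeding, because Section 8.3 provides one through suspension of accrual. What is missing is a scheduled review or hold after six and, for deaths, any mention of the DSMB. A reader might also infer that the rules lapse once patient 12 enrols. No section says so; the documents show only that the stated action then has nothing to act on. A count of five bleeds in twelve does not reveal a missing boundary either, since it implies at least four among the first eleven, which is already a trigger.

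The defence does not reconcile the sections. The synopsis still makes accrual to twelve conditional on the first six alone. Section 11 still links only the six-patient review to the stopping rules, with extra meetings dependent on monthly reports. Individual hold criteria and serious adverse event reporting protect individual patients, but they do not replace a stated response to a crossed boundary.

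**Conclusion.** The point holds as an inconsistency between sections, not as an error in the Section 8 calculation. The exact result needs no assumption beyond independent patients with a common event rate: the second boundary supplies 37-47% of the printed bleeding probabilities and 47-63% of the mortality probabilities. The six-patient-only values of 0.10/0.26/0.46 and 0.42/0.11 are a worst case, reached only if the synopsis and Section 11 are followed literally and continual monitoring is ignored. With Section 8 applied as written, the shortfall comes from the outcome lag alone. It is modest at slow accrual and larger at fast accrual, and the ranges in the working rest on assumed accrual and onset. The printed figure of seven cannot be called wrong, since it agrees with immediate outcomes and the documents do not fix the accrual rate.

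Two gaps remain under any reading: no stated action for a crossing recognised after patient 12 enrols, and no DSMB review named for the mortality boundary. Because safety is the trial's primary question and the remedy is cheap, the sections should be brought into line.

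**What to change.** 1. In the synopsis and Section 11, state that both boundaries in Sections 8.3 and 8.4 apply throughout accrual, not only to the first six patients.
2. State in Sections 8.3, 8.4 and 11 that a crossing of either the bleeding or the mortality boundary, at any time up to the last patient's Day 14, triggers prompt ad hoc DSMB review as well as suspension of any remaining accrual.
3. Label 0.19/0.47/0.73, 0.80/0.30 and the expected accrual of seven as assuming patient-by-patient looks with immediate outcomes. Alternatively, recompute them for the procedure actually run, with the accrual rate and any enrolment hold stated.

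The cost is amendment wording in the synopsis and Sections 8 and 11, a short recalculation if that option is chosen, and possibly one extra DSMB call. Recomputed figures would look slightly less favourable. No dose or treatment rule changes.

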### 2.0 HYPOTHESIS

Severe SARS-CoV2 infections are associated with the development of acute respiratory distress syndrome in the setting of hypercoagulability, endothelial dysfunction / thrombotic microangiopathy. Defibrotide therapy for patients with severe SARS-CoV2 ARDS will be safe and associated with improved overall survival, within 28 days of therapy initiation.

Rationale: To date, therapy for SARS-CoV2 lung injury has focused on agents that either inhibit viral replication and/or blunt the cytokine release syndrome associated with viralmediated immune activation. Only recently have we begun to realize that the lung injury associated with SARS-CoV2 infections are frequently associated with a ventilationperfusion mismatch, in which patients have preserved lung compliance, but impaired oxygenation. This raises a new paradigm in SARS-CoV2 therapy. Given the abnormal ventilation-perfusion mismatch with preserved compliance, it is thought that patients with SARS-CoV2 infections exhibit a loss of the normal hypoxic vasoconstriction reflex that helps preserve ventilation-perfusion matching (Gattinoni). This observation in conjunction with the frequent concurrence of multi-organ dysfunction (e.g. renal, hepatic) and hypercoagulability with marked elevations in D-dimer and PAI-1 levels in affected patients, support a dysfunction in the endothelium, and thus we hypothesize that this endothelial dysfunction is a prime target for SARS-CoV2 therapy. The current protocol will examine this hypothesis, utilizing an endothelial stabilizing agent (defibrotide). The agent is currently approved by the Food and Drug Administration (FDA) for use in patients with sinusoidal obstruction syndrome (SOS) with pulmonary or renal dysfunction following hematopoietic cell transplantation (HCT). In summary, the current trial is a feasibility trial, to assess the safety and tolerability of this regimen in this patient population.

The significance of this safety study is high. If successful, this trial will form the foundation for a multicenter, phase 2 trial targeting patients with viral induced ARDS.

#### 3.0 OBJECTIVES

#### 3.1 Primary Objective

To assess the safety and tolerability of defibrotide for the management of SARS-CoV2 related ARDS.

# 3.2 Secondary Objectives

To assess the therapeutic response of defibrotide therapy for patients with SARS-CoV2 related ARDS, including: Day 14, ventilator free survival.

- a. The number of ventilator free days within 14 days of study entry.
- b. The time to improvement in oxygenation, with improvement in oxygenation defined as an increase in PaO2/FiO2 of 50 (or greater) compared to the nadir of PaO2/FiO2.
- c. To use the "WHO COVID-19 Ordinal Scale" to assess the mean change in the WHO scores during study therapy.
- d. Overall Survival at 28 days.

# 3.3 Exploratory Objectives:

To perform preliminary assessment of endothelial biomarkers in patients with SARS-CoV2 ARDS, with correlation to serum cytokines and clinical response.

#### 4.0 BACKGROUND

**General (SARS-CoV2):** Coronavirus Disease 2019 (COVID-19), caused by a novel coronavirus (SARS-CoV2), is a highly infectious pathogen that spreads primarily through respiratory droplets and/or aerosol particles. Though many affected patients express only mild symptomatology, with fever, cough and myalgias / fatigue, approximately10-20% of patients may develop a more severe phenotype with rapid progression to acute respiratory distress syndrome (ARDS), septic shock, disseminated intravascular coagulation (DIC) and hypercoagulability. Older age and co-morbid conditions (obesity, diabetes, immunocompromised, etc) are known risk factors for a more severe disease phenotype (Chen N 2020)(Huang C 2020).

**Pulmonary Complications associated with SARS-CoV2:** Emerging data from centers caring for patients affected with SARS-CoV2, suggest a significant component of endothelial dysfunction and dysregulation of thrombotic/fibrinolytic pathway. Mechanical ventilation in patients with SARS-CoV2 lung injury demonstrate good compliance but severe hypoxemia unlike patients with traditional ARDS, which is typically characterized by significant stiffness and reduction in lung compliance. The severe hypoxemia is attributed to high shunt (>50%), hypoxic vasoconstriction, and microvascular thrombosis in the pulmonary circulation, ultimately leading to ventilatory dead space (Wu 2020)(Xu 2020). The acute precipitous decline in respiratory status of these patients is also linked to inflammatory mediators and "cytokine storm" with a recent retrospective, multicenter study of 150 confirmed COVID-19 cases in Wuhan, China, demonstrating decreased survival with elevated ferritin (mean 1297-6 ng/ml in non-survivors *vs* 614-0 ng/ml in survivors; p<0.001) and IL-6 (p<0.0001).

**Coagulopathy in SARS-CoV2 ARDS: Incidence.** The incidence of SARS-CoV2 related coagulopathy is only now being understood, with thrombotic complications reported in 30-35% of affected patients. A current Dutch publication (April 6th, 2020) examined 184 ICU patients with proven SARS-CoV2 ARDS, with a cumulative incidence of thrombotic complications of 31% (95%CI: 20-41), including both arterial thrombotic and pulmonary emboli (Kluk FA 2020). All patients developed thrombotic complications despite standard heparin thrombo-prophylaxis.

Even heparinization in this patient population may NOT prevent thrombotic complications. A study of 26 patients with SARS-Cov2 ARDS in two European intensive care units (ICU) was reported in April 2020, with patients receiving either prophylactic (31%) or therapeutic anticoagulation (69%) for venous thromboembolism prevention (Llitjos 2020). Patients received either low molecular weight or unfractionated heparin, with anti-Xa levels monitored. The overall incidence of thromboembolic complications was 69%, significantly higher in patients treated with prophylactic vs therapeutic heparin (100% vs. 56%, respectively, p=0.03).

Coagulopathy in SARS-CoV2 ARDS: Pathophysiology. Emerging data from centers caring for patients infected with SARS-CoV2 suggests a significant component of endothelial dysfunction and dysregulation of thrombotic/fibrinolytic (Hunt2020)(Thachil 2020)(Nascimento I 2020)(Huang 2020)(Tang 2020). Severe SARS-CoV2 infections, in particular, have been associated with markedly elevated D-dimers levels, with increasing mortality as the D-dimer rises. Day 28 mortality rates of 52.4% have been reported with D-dimer values > 6-fold upper limit of normal (ULN), with mortality approaching 60% with D-dimers > 8 fold ULN (Yin 2020). Of note, hemorrhagic symptomatology are not common with SARS-CoV2 infections, with infrequent reports of pulmonary or gastro-intestinal bleeding (Thachil 2020)(Hunt 2020) in affected patients. Interestingly enough, thrombocytopenia is rarely noted, with < 5% of severely affected patients exhibiting a platelet count < 100,000/uL on admission (Thachil 2020), with hyperfibrinogenemia (not hyofibrinogenemia) commonly described. Thrombo-prophylaxis with anticoagulants (heparin and/or low molecular weight heparin, LMW Heparin) have been shown to decrease mortality in patients with severe SARS-CoV2 infections (Yin 2020). This is especially true in patients with sepsis induced coagulopathy (SIC) scores ≥4 (40.0% vs 64.2%, P=0.029) and patients with markedly elevated D-dimer (> 3.0 mcg/ml, or > 6-fold the upper limit of normal).

There is ample evidence to suggest that fibrin deposition is a key feature of SARS-CoV2 related ARDS, with markedly elevated levels of plasminogen activator inhibitor-1 (PAI-1), a critical regulator of fibrinolysis, noted (Giannis 2020). A role for platelet and megakaryocyte activation in viral mediated illnesses has been previously shown, with evidence that coronaviruses directly infect megakaryocytes, and activate platelet function (Yang 2005). A recent lung autopsy series of patients infected in the United States with SARS-CoV2 noted an abundance of megakaryocytes, platelet-rich thrombi, pulmonary vascular microthrombi, and downstream foci of hemorrhage. A notable finding was the lack of significant secondary infection in these cases, suggesting that secondary infections were not the cause of mortality (Fox 2020). The authors concluded that effective therapy for patients with SARS-CoV2 ARDS should not only target the viral pathogen, but also the thrombotic and microangiopathic effects of the virus (Fox 2020).

**Defibrotide:** Rationale and Mechanism of action. Defibrotide (DF) is a polydeoxyribonucleotide that was FDA approved in March 2016 for the treatment of

sinusoidal obstruction syndrome (SOS) with pulmonary and renal dysfunction following hematopoietic cell transplant (HCT), with significant improvement in day 100 post-HCT survival noted in treated subjects (Richardson 2016). Defibrotide displays significant anticoagulant, anti-inflammatory, and endothelial cell protective properties (Kornblum 2006)(Larocca 2008)(Richardson 2009)(Bianchi 1993).

Though the mechanism of action of DF is not yet completely understood, it is clearly related to its polyanionic nature, interaction with plasma and/or matrix proteins, binding to adenosine receptors (ARs), and protection of the vascular endothelium. A number of in vitro studies have demonstrated that DF blocks tissue factor and plasminogen activator inhibitor-1 (PAI-1) expression induced by lipopolysaccharide (LPS) in endothelial cells (Cella 2001). Dendritic cells, a key mediator in the coagulation-inflammatory pathway serve as a novel target for DF, with DF shown to actively inhibit Toll-like receptors on macrophages and dendritic cells (Franchischetti 2012). Following therapy with DF, marked decreases in PAI-1 levels have been reported in therapy responders, with PAI-1 levels typically unchanged in non-responders (Kaleelrahman 2003). Common toxicities related to DF have included hemorrhagic and/or hypotensive events, though the incidence of pulmonary hemorrhage [11.8% and 15.6%] and gastrointestinal bleeding [7.8% and 9.4%] were similar between DF and control groups in the licensing trial (Richardson 2016). We are now proposing an open label, trial of defibrotide for patients with severe SARS-CoV2 with acute respiratory distress syndrome.

**Defibrotide (DF) vs heparin for thrombo-prophylaxis:** Several studies have shown that DF is at least as effective, or potentially more effective than heparin (Rizzi 1987) (Strouse 2016). A large, open-label, multicenter study in post-op patients (n=4810), in which defibrotide (n = 2810) vs heparin prophylaxis (n=2000) was administered noted that the incidence of postsurgical DVT and pulmonary embolism (PE) were significantly lower in the defibrotide arm [1.17 vs 2.35% (DVT), p = .002; 0.53 vs 1.15%, p = .025 (PE), respectively] (Gerosa 1989).

**Defibrotide dosing**: Current FDA approved dosing schedules (25 mg/kg/day in 4 divided doses) were derived from pharmacokinetic (Pk) studies in healthy controls, subjects with hepatic SOS and those with hepato-renal dysfunction (Tocchetti 2016)(Umemura 2016)(Palmer 1993). Peak levels and peak pharmacodynamics effects are noted following 2-hours of infusion, with rapid clearance and short half-life (<1.0 hours)(Umemura 2016). Similar pharmacokinetic profiles are seen in subjects with end-stage renal disease and/or patients undergoing hemodialysis (Tocchetti 2016). Thus, renal impairment does not impact clearance or dosing schedule, with 25 mg/kg/day still administered in 4 divided doses. The current protocol will utilize this same dosing schedule. The frequent association of renal dysfunction with SARS-CoV2 ARDS will not lead to any dosing adjustments.

In summary, SARS-CoV2 induced changes in the fibrinolytic pathway are global in nature, impacting the coagulation-inflammatory pathway. Defibrotide may serve as a potent anti-coagulant, pro-fibrinolytic and endothelial stabilizing agent, potentially playing a key role in lessening thrombo-embolic disease and multi-organ dysfunction associated with this disorder. We hypothesize that through its role in preventing pulmonary microthrombi, decreasing pulmonary endothelial production of inflammatory cytokines (IL-1, IL-6, TNFR1, IL-8), promoting vaso-dilation (increased production of nitric oxide, prostanoids), ability to restore normal endothelium induced vascular responses, inhibition of platelet activation

(reduction in VWF), and regulation of the fibrinolytic pathway (reduction in PAI-1), defibrotide will lead to improvement in oxygenation and promote the resolution of ARDS. The high incidence of renal and cardiac dysfunction in SARS-CoV2 affected patients may be similarly impacted.

